7.5 SECONDARY OBJECTIVE ANALYSIS

7.5.1 Key secondary objective analysis

For part I, this section is not applicable as no key secondary endpoint has been specified in the protocol.

7.5.2 Secondary objective analysis

For part 1, for each of the secondary endpoint, treatment policy will be used as the primary strategy to handle intercurrent events as for the primary endpoint.

Continuous secondary endpoints

All secondary endpoints for part 1 are continuous endpoints, which will be analyzed using a MMRM approach based upon the model specification similar as described for the primary endpoint. Also, absolute change from baseline in IHS4 at week 8 is selected to use MCPMod to demonstrate a non-flat dose response curve.

SAS code for MMRM for the endpoint of IHS4:

The following SAS code will be used to calculate the MMRM.

PROC MIXED DATA=all at cl method=reml;

CLASS dt base categorical visit trt TNFi subject;

[figure not shown]
MODEL ept = TNFi dt base categorical visit*trt base*visit/ddfm=kr s CL;

REPEATED visit / subject= subject type=un r rcorr;

LSMEANS visit*trt / pdiff=all om cl alpha=0.05 slice=visit;

[figure not shown]
RUN;

Date: 07-08-2024, Version 1.0

c43421787-01

c43421787-01

Proprietary confidential information © 2024 Boehringer Ingelheim International GmbH or one or more of its affiliated companies.

7.7 EXTENT OF EXPOSURE

The exposure to study medication will be analyzed based on SAF. The number of subjects who received a dose of trial drug will be tabulated. The amount of total dose and duration of exposure will be summarized by descriptive statistics (N, mean, SD, minimum, median, maximum) for the overall on-treatment period, the loading stage, whole maintenance stage, maintenance stage I, maintenance stage II, maintenance stage III as described in Table 6.1:1. The duration of exposure will also be summarized with the following categories:

<= to <= 8 weeks
> 8 weeks to <= 16 weeks
> 16 weeks to <= to <= to <=
to <=

7.8 SAFETY ANALYSIS

All safety analyses will be performed on the SAF following BI standards. Data will be summarized descriptively without any imputation based on data available.

As the onset time of an AE will not be collected in the trial, any AE which occurs on the same day as a treatment dose will be assigned to the on-treatment period defined in Table 6.1:1. For safety assessments by visits, if time is not collected, data on the same day of a treatment dose will be treated to be "prior treatment" except for scheduled local tolerability and post-dose vital signs assessments.

Off-treatment data will be listed only.

7.8.1 Adverse Events

Date: 07-08-2024, Version 1.0

Unless otherwise specified, the analyses of AEs will be descriptive in nature, which will include all on-treatment events up to week 8, week 16 treatment, as well as all events during the whole on-treatment period respectively. All analyses of AEs will be based on the number of subjects with AEs and NOT on the number of AEs.

AEs will be coded with the most recent version of MedDRA®. Patients will be analyzed according to the actual treatment received.

The analysis of AEs will be based on the concept of treatment emergent adverse events (TEAE). That means that all AEs occurring between first drug intake till 112 days after last drug intake will be assigned to the on-treatment period. All AEs occurring before first drug intake will be assigned to 'screening' and all AEs occurring after last drug intake + 112 days will be assigned to 'follow-up' (for listings only). For details on the treatment definition, see Table 6.1:1.

The exposure adjusted incidence rate (per 100 patient years) of a selected treatment emergent adverse event is defined as the number of patients experiencing the adverse event per

Proprietary confidential information © 2024 Boehringer Ingelheim International GmbH or one or more of its affiliated companies.

treatment group during time at risk divided by the total time of patients at risk in that treatment group to contribute the event to the analysis multiplied by 100 (per 100 patient years).

Time at risk [patient years] = (date of onset of AE– first treatment start date within that treatment period + 1) / 365.25

If, for a patient, the selected treatment emergent adverse event didn't occur during the above defined treatment period (per Table 6.1:1) then the time at risk will be censored at the earliest of date of death, last contact date per EoS page, or the end of the above defined treatment period.

For each selected treatment emergent AE, the exposure adjusted incidence rate will be calculated as:

Incidence rate [1/100 Patient years (pt-yrs)] = 100 * number of patients with TEAE / Total TEAE-specific time at risk [patient years].

The analyses of AEs will be descriptive in nature. Analyses of AEs will be based on the exposure adjusted incidence rates (per 100 patient years), as well as the number of patients with AEs. System organ classes (SOCs) (if applicable) will be sorted according to the standard sort order specified by the European Medicines Agency (EMA), preferred terms (PTs) (if applicable) will be sorted by total frequency (within SOC).

For further details on summarization of AE data, please refer to "Handling and summarization of adverse event data for clinical trial reports and integrated summaries" (9.8) and "Handling of missing and incomplete AE dates" (9.1).

An overall summary of AEs will be presented. This overall summary will also include summary for the class of investigator reported AESIs.

The following are considered as AESIs (see Sec 5.2.6.1 of CTP):

- Systemic hypersensitivity including infusion reaction and anaphylactic reaction
- Severe infections (according to CTCAE grading in Section 15 of the ISF)
- Opportunistic and mycobacterium tuberculosis infections
- Potential Severe Drug Induced Liver Injury (DILI)
- Peripheral neuropathy

Date: 07-08-2024, Version 1.0

In addition, user defined adverse event concepts (UDAEC) identified through specific search criteria will be reported separately (see Table 7.8.1:1).

c43421787-01

Table 7.8.1: 1 Project MEDDRA search criteria for User Defined Adverse Events Concepts

User-defined .	AE category	Category			
Hypersensitivity					
	Hypersensitivity ALL	All of the categories below			
	Anaphylactic reaction, narrow	Narrow SMQ "Anaphylactic reaction"			
	Angioedema, narrow	Narrow SMQ "Angioedema"			
	Hypersensitivity, narrow	Narrow SMQ "Hypersensitivity"			
Infections (serio	us/severe, opportunistic)				
	Infections 'ALL'	All of the categories below			
	Opportunistic infections	Narrow SMQ "Opportunistic infections"			
	Tuberculosis infections	Sub-BIcMQ "Tuberculosis related terms", narrow BIcMQ "Infections", narrow sub-search 8.2 "Tuberculosis related terms"			
	Severe infections	SOC "Infections and infestations" with AETOXGR >= 3 OR AESEV = 'Severe'. Not derived for studies where both severity variables are collected. SOC "Infections and infestations" – AEs of at least			
	Serious infections	severe CTCAE grade (>= 3) or any severe events SOC "Infections and infestations" with [AECOND: AESER =1] SOC "Infections and infestations" – SAEs			
Malignancies					
	Malignant tumours	Narrow sub-SMQ "Haematological malignant tumours",			
		Narrow sub-SMQ "Non-Haematological malignant tumours"			
		Narrow Sub-SMQ "Malignant tumours"			
	Malignant skin tumours	Broad Sub-SMQ "Skin malignant tumours"			
	Skin melanomas	HLT Skin melanomas (excl. Ocular)			
	Non-melanoma skin cancer (NMSC)	Broad Sub-SMQ "Skin malignant tumours" excluding HLT Skin melanomas (excl. Ocular)			
	Malignancies excluding non- melanoma skin cancer (NMSC)	Sub-SMQ "Malignant tumours" excluding NMSC defined above			
3 - point MACI	E for Monitoring				
	3-point MACE for Monitoring	BIcMQ "Major Adverse Cardiovascular Events" wit Narrow sub-search 1.1 "3-point MACE (part1/2) for monitoring"			
		Narrow sub-search 1.2 "3-point MACE (part2/2) for monitoring" and AE outcome=fatal *			
Depression					
	Depression	Broad sub-SMQ "Depression (excl suicide and self-injury)"			
Suicidal ideation	and behavior (SIB)				
	sub-SMQ "Suicide/self-injury"	sub-SMQ "Suicide/self-injury"			

Proprietary confidential information © 2024 Boehringer Ingelheim International GmbH or one or more of its affiliated companies.

User-defined AE category		Category		
DRESS#				
	Narrow DRESS (Drug reaction with eosinophilia and systemic symptoms syndrome)	Narrow SMQ "Drug reaction with eosinophilia and systemic symptoms syndrome"		
Peripheral N	europathy, Narrow			
-	Guillain-Barré Syndrome	Narrow SMQ "Guillain-Barré syndrome"		
	Peripheral Neuropathy	Narrow SMQ "Peripheral Neuropathy"		
	Demyelination	Narrow SMQ "Demyelination"		

^{*} This is achieved by retrieving all cases found either by running subsearch 1 in narrow scope (BIcMQ search ID 32019093) or subsearch 2 (BIcMQ serach ID 32019094).
DRESS algorithmic search will be presented as a listing.

According to ICH E3 (9.9), in addition to Deaths and serious adverse events, 'other significant' AEs need to be listed in the clinical trial report. These will be any non-serious adverse event that led to an action taken with study drug (e.g. discontinuation or dose reduced or interrupted). An overall summary of adverse events will be presented.

The frequency of subjects with AEs will be summarized by treatment, primary system organ class and preferred term. AEs which were considered by the investigator to be drug related will be summarized separately. Separate tables will also be provided for subjects with SAEs, subjects with AEs leading to study drug discontinuation, subjects with AESIs, subjects with other significant AEs (derived based upon ICH E3 (9.9)), User-defined Adverse Event Concepts (UDAEC) (Table 7.8.1:1) and serious UDAEC. AEs will also be summarized by maximum intensity based on the CTCAE grading system.

For disclosure of AE data on ClinicalTrials.gov, the frequency of subjects with non-serious AEs occurring with an incidence of greater than 5% (in preferred terms) will be summarized by treatment, primary system organ class and preferred term. The frequency of subjects with SAEs will also be summarized.

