#### Screening and randomisation After signing the informed consent, trial participants will enter the screening period for up to 28 days, and if all eligibility criteria are met, trial participants will be randomised in a ratio to either active group, including high dose, medium dose, and low dose group, or placebo group The randomisation will be stratified for and baseline For stratification, the details are described in Section 7.4. At least approximately participants from population (meaning a corresponding and a maximum of approximately participants from population (meaning a corresponding are planned to be randomised, respectively. These participants who were might have had a primary or a secondary failure of previously Primary failure of is defined as lack of efficacy after at least 3 months of treatment with an agent (patients who never responded), and secondary failure is defined as loss of clinical efficacy in a trial participant after initial response to an agent (patients who initially responded but then relapsed). Additionally, might have due to AE or stopped for other reason. Approximately participants with baseline and participants with baseline are planned to be randomised, respectively. No stratification beyond those prior described will be applied for the trial participants. Study in the Flowchart represents the is used for Day 1.

Boehringer Ingelheim BI Trial No.: 1368-0098

c40061625-02 Clinical Trial Protocol Page 47 of 177

Proprietary confidential information © 2023 Boehringer Ingelheim International GmbH or one or more of its affiliated companies

Treatment phase Once randomised, trial participants will start a treatment period of Administration of treatment will be up to The final assessment of treatment effect will be on (EoT visit).
For the first according to the assigned dose group, trial participants will be administered an initial dose of spesolimab high dose group], at Visit 2 Visit 3 Visit 4 , and Visit 5 or matching placebo.  From Visit 6 to Visit 9 (both inclusive), trial participants will be administered a group], or medium dose group], or medium dose group], or medium dose group], or matching placebo. For trial participants initially randomised to spesolimab group, from Visit 10 to Visit 31 (both inclusive), the participants will be administered a dose of spesolimab: either (high and medium dose group) or low dose group)  [Indicate the assigned dose group] according to the assigned dose group).

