# 5.2.6.2.1 AE collection

The investigator shall maintain and keep detailed records of all AEs in the participant files.

Per default SAEs/AESIs should be reported via the eCRF in the EDC system. If the EDC system is not or no longer available (e.g. after database lock), the BI paper SAE form should be used; please see Section 5.2.6.2.2.

For trial participants not rolling over to LTE trial, the following must be collected and documented on the appropriate CRF(s) by the investigator:

- From signing the informed consent onwards until the individual participant's end of trial (usually the EoS visit, please see Section 6.2.3): all AEs (serious and non-serious) and all AESIs
- After the individual participant's end of trial: the investigator does not need to actively monitor the participant for new AEs but should only report any occurrence of cancer of new histology and trial drug-related SAEs and trial drug-related AESIs of which the investigator may become aware of by any means of communication, e.g. phone call; those AEs should be reported on the BI SAE form (see Section 5.2.6.2.2), but not on the CRF

For trial participants rolling over to LTE trial the following must be collected and documented on the appropriate CRF(s) by the investigator or delegated:

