#### 7.2.6 Safety analyses

Adverse events will be coded using the Medical Dictionary for Drug Regulatory Activities (MedDRA). Standard BI summary tables and listings will be produced. All adverse events with an onset between start of treatment and end of the REP, a period of 16 weeks after the last dose of trial medication, will be assigned to the on-treatment period for evaluation.

The safety analysis will be performed by treatment at onset.

Safety analyses will be based on the TS. In general, safety analyses will be descriptive in nature and will be based on BI standards. No hypothesis testing is planned.

Statistical analysis and reporting of adverse events will concentrate on treatment-emergent adverse events, i.e. all adverse events occurring between start of treatment and end of the REP. Adverse events that start before first drug intake and deteriorate under treatment will also be considered as 'treatment-emergent'. Adverse events will be summarized by treatment at onset, and the treatment at onset of AE for the drug-related AE.

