4. CHANGES IN THE PLANNED ANALYSIS OF THE STUDY

All analyses stated in the CTP (latest version) will be performed as planned with the following adaptations.

The below further efficacy endpoints have been updated:

- Achievement of HiSCR50 at each scheduled assessment.
 HiSCR50 is defined as at least a 50% reduction from baseline in the total abscess and inflammatory nodule count, with no increase in the abscess or draining fistula count.
- Absolute change from baseline in Patient Global Impression of Change (PGI-C) score over time.

This endpoint will be updated to:

Patient Global Impression of Change (PGI-C) score at each scheduled assessment over time.

• Absolute change from baseline in Patient Global Impression of Severity (PGI-S) score over time.

This endpoint will be updated to:

Date: 07-08-2024, Version 1.0

Patient Global Impression of Severity (PGI-S) score at each scheduled assessment over time.

The below further efficacy endpoints, which were not specified in the CTP version 2.0, have been added:

- Achievement of HiSCR75 at each scheduled assessment.
 HiSCR75 is defined as at least a 75% reduction from baseline in the total abscess and inflammatory nodule count, with no increase in the abscess or draining fistula count.
- Achievement of HiSCR90 at each scheduled assessment.
 HiSCR90 is defined as at least a 90% reduction from baseline in the total abscess and inflammatory nodule count, with no increase in the abscess or draining fistula count.
- Achievement of mHiSCR at each scheduled assessment: mHiSCR is defined as at least a 50% reduction in total ANdT count relative to baseline. and at least 50% reduction in total dT count relative to baseline.
- Achievement of mHiSCR-AdT at each scheduled assessment: mHiSCR-AdT is defined as at least a 50% reduction in the total AdT count with no increase in inflammatory nodule count, no increase in abscess count, and no increase in dT count relative to baseline.
- Achievement of mHiSCR-AdT(2) at each scheduled assessment: mHiSCR-AdT (2) is defined as at least 50% reduction in the total ANdT count relative to baseline and at least 50% reduction in total AdT count relative to baseline.

Boehringer Ingelheim TRIAL STATISTICAL ANALYSIS PLAN 1368-0098

Date: 07-08-2024, Version 1.0

Page 10 of 64

c43421787-01

- Achievement of 2 points reduction in Physician's Global Assessment (PGA) score from baseline at each scheduled assessment (only for patients with a PGA \geq 2 at baseline).

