5.2.2 Secondary endpoint(s)

Part 1 (Phase IIb) Efficacy

Date: 07-08-2024, Version 1.0

[figure not shown]
- Percent change from baseline in dT count at Week 16.
- Absolute change from baseline in IHS4 value at Week 8.
- Absolute change from baseline in IHS4 value at Week 16.

Safety

[figure not shown]
Occurrence of treatment emergent adverse events (TEAEs)

[figure not shown]
c43421787-01

[figure not shown]
c43421787-01

[figure not shown]
c43421787-01

c43421787-01

c43421787-01

Proprietary confidential information © 2024 Boehringer Ingelheim International GmbH or one or more of its affiliated companies.

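### SAP 7.8.1 defines treatment-emergent adverse events by date alone and drops, without declaring it, the protocol rule that pre-dose events deteriorating under treatment also count

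*SAP*

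**What the plan says.** **Protocol 7.2.6** places events on treatment when they begin between the first dose and the end of the residual effect period, "a period of 16 weeks after the last dose of trial medication". It then adds a second route into the definition: "Adverse events that start before first drug intake and deteriorate under treatment will also be considered as" treatment-emergent.

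**SAP 7.8.1** says the analysis rests on the TEAE concept and explains what that means: "all AEs occurring between first drug intake till 112 days after last drug intake will be assigned to the on-treatment period". The next sentence deals with earlier events: "All AEs occurring before first drug intake will be assigned to" the screening category. Deterioration is not mentioned.

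**SAP section 4** opens with "All analyses stated in the CTP (latest version) will be performed as planned with the following adaptations". The adaptations that follow are all efficacy endpoints.

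**SAP 5.2.2** lists occurrence of TEAEs as the one safety item among the Part 1 secondary endpoints.

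**The concern.** The two current documents give different membership rules for the same endpoint, and a reader of SAP section 4 would not learn of it. The events on which they differ are, by definition, those that got worse after dosing began, and a TEAE rule exists to capture those.

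The overall proportion with any TEAE is not the only output at stake. SAP 7.8.1 and 7.8.2 build further displays on the same concept: drug-related events, serious events, events of special interest, the user-defined categories, maximum CTCAE grade and exposure-adjusted incidence rates. For a rare category, one participant can change the table.

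One display shows the effect concretely. The third hepatic alert in protocol 5.2.6.1.4 combines an AST or ALT elevation with new or worsening symptoms such as nausea or fatigue. The matching display in SAP 7.8.2 requires the symptom to be a TEAE. Nausea that began in screening and worsened on treatment under the same record would not satisfy that condition, so the case would not be flagged by that route.

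**Working it through.** The documents give no figure on this point, so the check is a comparison of texts, plus one arithmetic test of whether the SAP could apply the protocol rule as it stands.

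**1. End of the window.** Protocol: 16 weeks after the last dose. SAP: 112 days. 16 × 7 = 112, so they agree.

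**2. Start of the window.**

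| Event | Protocol 7.2.6 | SAP 7.8 and 7.8.1 |
|---|---|---|
| Onset after first dose, within the window | Treatment-emergent | Treatment-emergent |
| Dated Day 1, clock time unknown | Not addressed | On-treatment (onset time is not collected) |
| Onset before Day 1, no deterioration | Not treatment-emergent | Screening |
| Onset before Day 1, deteriorates under treatment | Treatment-emergent | Screening |

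Only the last row is in conflict.

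**3. Can such events occur?** Yes. Protocol 5.2.6.2.1 collects adverse events "From signing the informed consent onwards until the individual" participant's end of trial, and under protocol 3.1 "trial participants will enter the screening period for up to 28 days". The exposed set is events starting between consent and the day before the first dose.

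**4. Does other SAP text restore the rule?** No.
- Table 6.1:1 ends screening one minute before the first dose.
- Section 6.7 says adverse event frequency tables use on-treatment data sorted by when events occur or start.
- Section 4 declares nothing on the matter.
- Section 7.8.1 refers to a company document (reference 9.8) for further detail on summarising adverse events. Its content is not available here.

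**5. Could the SAP apply the protocol rule without further text?** Time at risk in SAP 7.8.1 is (event onset date − first treatment start date in the period + 1) / 365.25.
- Onset 10 days before the first dose: (−10 + 1) / 365.25 = −0.025 patient-years.
- Onset 1 day before: (−1 + 1) / 365.25 = 0.

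Any pre-dose onset gives zero or negative time at risk, so restoring the clause also requires a rule for the date.

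**6. Size, by assumption only.** None of these inputs comes from the documents. Suppose 10–20% of participants have an event ongoing at the first dose and 5–15% of those worsen under the same record.
- Participants losing a TEAE record: 0.10 × 0.05 = 0.5% to 0.20 × 0.15 = 3%.
- If 60–80% have another TEAE anyway, independently, the any-TEAE proportion falls by 0.005 × 0.20 = 0.1 to 0.03 × 0.40 = 1.2 percentage points.
- The count for an affected preferred term falls by every such participant with no other TEAE under that term.

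**The case against.** The strongest reply is that the protocol clause still governs. The SAP says it elaborates protocol section 7, assumes familiarity with it, and performs the protocol analyses as planned apart from listed adaptations. On that view 7.8.1 restates only the period-assignment rule and leaves the deterioration clause in force. This does not fit the text. The SAP gives its explanation as the meaning of the TEAE concept and then assigns all earlier events elsewhere. A programmer working from it would have no reason to add an exception.

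Two further points stand as limits on the consequence. Protocol 5.2.6.1.1 asks for worsening of the underlying disease and of other pre-existing conditions to be recorded. If sites enter that as a new event, its onset falls after the dose and the SAP counts it. The company standard cited in 7.8.1 may also deal with worsening. The documents settle neither point, and an unseen general standard cannot be assumed to override explicit SAP wording.

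Some stronger readings are tempting but not supported:
- **That the endpoint is undercounted as a matter of fact.** Loss of events depends on literal programming and on worsening staying on the pre-dose record.
- **That every event starting before the dose is confined to listings.** Events dated Day 1 are on-treatment, and the listings-only remark in 7.8.1 most naturally belongs to the follow-up category. Screening events are still outside the on-treatment tables.
- **That serious cases would disappear.** Under SAP 7.8.1, deaths and serious events are still listed in the trial report. Exclusion criterion 10 (active systemic infection within 2 weeks of Visit 2) also narrows one route to a screening-onset severe infection.

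**Conclusion.** The conflict is certain: the SAP's stated rule differs from the protocol's for the only listed Part 1 secondary safety endpoint, and section 4 does not say so. Followed literally, the SAP leaves a screening-onset event that worsens on treatment under its existing record out of the TEAE tables and the displays derived from them.

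The numerical effect is unknown and probably small, because only events starting between consent and the day before the first dose are exposed. It could be nil under either of the mitigations above. Safety analysis here is descriptive, so no test or error rate is affected. The point should be corrected because the affected events are those that worsened on treatment and the repair is cheap. It does not put the trial's conclusions in doubt.

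**What to change.** In SAP 7.8.1, restore the protocol's deterioration clause and add two statements:

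1. How deterioration is identified from the recorded adverse event data. The protocol says only that the event deteriorates, and protocol 5.2.6.1.5 requires a CTCAE grade without saying whether grade changes over time are captured. A rise in grade or a change to serious is one possible rule, but the sponsor has to choose it.
2. Which date stands in for onset, for example the date of worsening, in both period assignment (Table 6.1:1) and the time-at-risk formula.

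If worsening is to be entered as a new event, or if reference 9.8 already covers it, say so in the same place. If the narrower definition is intended, declare and justify it in section 4 instead.

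The cost is a few sentences and at most one derivation, provided the adverse event record holds what is needed to identify and date worsening. If it does not, a convention has to be agreed before treatment information is released.
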